6. CLINICAL TRIAL OBJECTIVES

6.1. Primary Endpoints

Safety: Freedom from major adverse events (MAEs) at 30 days post index procedure, as adjudicated by the Clinical Events Committee (CEC) or core laboratory including:

- Device or procedure-related death
- Device or procedure-related bleed at the target vessel and/or the target lesion or at the access site requiring surgical or endovascular intervention or blood transfusion of ≥ 2 units
- Device or procedure-related venous injury occurring in the target vessel and/or the target lesion or at the access site requiring surgical or endovascular intervention
- Major amputation of the target limb
- Clinically significant pulmonary embolism, confirmed by CT angiography
- Stent embolization outside of the target vessel
- Presence of new thrombus within the stented segment

Efficacy: Primary patency of stented segment at 12 months defined as freedom from:

- Duplex Ultrasound (DUS) core laboratory adjudicated occlusion or stenosis $>50\%$ within the stented segment. If site reported or core laboratory adjudicated DUS shows $>50\%$ stenosis or occlusion, confirmation by diagnostic IVUS is required.
- CEC adjudicated clinically driven target lesion reintervention (CD-TLR) defined as endovascular or surgical procedure for new, recurrent, or worsening symptoms and core lab adjudicated $>50\%$ stenosis or occlusion within the stented segment confirmed by diagnostic IVUS

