16. In DVT subjects, successful treatment of acute thrombus must have occurred prior to receiving any DUO Stents for an underlying obstructive lesion. Successful treatment of acute thrombus is defined as reestablishment of antegrade flow with $\leq 30\%$ residual thrombus (confirmed by venogram or IVUS) and freedom from bleeding and symptomatic pulmonary embolism (confirmed by imaging). After successful treatment of thrombus is confirmed, eligible obstructive lesion(s) can be treated with a DUO Stent during the same procedure.
17. All subjects must undergo a SARS-CoV-2 test and have a negative test result within 8 days prior to the index procedure. If a SARS-CoV-2 test is unavailable due to institution policy, a test shortage, or if there is a delay in test results, the subject must complete the COVID-19 questionnaire and must have answered NO to all questions to be eligible for enrollment. A SARS-CoV-2 test will not be required for enrollment if a subject has received a complete cycle of an authorized COVID-19 vaccine or has documented evidence of a positive COVID-

- 19 antibody test and is asymptomatic and has no long-lasting effects (per PI discretion) from a prior COVID-19 infection.
18. A measured temperature less than 99.5°F (37.5°C) on the day of the index procedure and no history of fever or feeling feverish within 14 days of the index procedure
19. No prior history, within 60 days of the index procedure, of a SARS-CoV-2 positive test, or COVID-19 symptoms

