16. RISK/BENEFIT ASSESSMENT

16.1. Risks

The use of the DUO Venous Stent System in treating venous obstructions may result in anticipated potential risks or complications similar to other available endovascular implant devices (such as stents) used in these procedures. Such risks are included in the DUO Venous Stent System IFU and are listed below:

- Access failure or abrupt closure
- Allergic/anaphylactoid reaction to anticoagulant and/or antithrombotic therapy or contrast medium
- Allergic reaction to Nitinol
- Amputation
- Aneurysm
- Angina/coronary ischemia/myocardial infarction
- Arrhythmia
- Arteriovenous fistula
- Death
- Embolism
- Emergent repeat hospital intervention
- Extravasation
- Fever
- Gastrointestinal bleed from anticoagulation/antiplatelet medication
- Hematoma/hemorrhage
- Hypotension/hypertension
- Incorrect positioning of the stent requiring further stenting or surgery
- Intimal Injury/dissection
- Ischemia/infarction or tissue/organ
- Infection/abscess at insertion site
- Inflammation
- Malposition of stent
- Multi-organ failure
- Open surgical repair
- Pain
- Pulmonary Embolism
- Pseudoaneurysm
- Renal insufficiency or failure
- Respiratory distress or failure
- Restenosis
- Rupture
- Septicemia/bacteremia (sepsis)
- Stent implant fracture
- Stent implant migration (device moves over time)
- Trauma to adjacent structures

- Vasospasm
- Venous occlusion/thrombosis, remote from puncture site
- Venous occlusion/thrombosis, near puncture site
- Venous occlusion/restenosis of the treated vessel

These risks are present in any endovascular treatment procedure for which the study subjects would be indicated because of their disease and will be reviewed with all subjects during the informed consent process.

16.2. **Potential Benefits**

- The DUO Stent may help improve the blood flow in the leg vein.
- Participation in this study may yield information that is necessary for the development of better or new treatments for this disease and may benefit other people who have the same blockages in the leg veins.

16.3. **Justification for Clinical Trial**

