17.4. Major Adverse Events

For this study, the definition of a MAE includes the following events that comprise safety and observational endpoints that require adjudication by the CEC:

- Device or procedure-related death
- Device or procedure-related bleed at the target vessel and/or the target lesion or at the access site requiring surgical or endovascular intervention or blood transfusion of ≥ 2 units
- Device or procedure-related venous injury occurring in the target vessel and/or the target lesion or at the access site requiring surgical or endovascular intervention
- Major amputation of the target limb
- Clinically significant pulmonary embolism, confirmed by CT angiography
- Stent embolization outside of the target vessel
- Presence of new thrombus within the stented segment

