The performance goals for both primary safety and primary effectiveness were established based on research in a pre-COVID-19 era and therefore do not account for potential increases in MAEs or decreases in patency associated with SARS-CoV-2 or COVID-19. For each of the hypothesis tests, the current plan is to use the same performance goal in all subjects and in the SARS-CoV-2 negative subgroup given that the potential effects due to SARS-CoV-2 are not well understood. This decision will be revisited prior to analysis of the study data. In the event that additional information becomes publicly available regarding SARS-CoV-2, as related to the VIVID study primary endpoints, we may summarize the major event rate and primary patency in the subject population without and with SARS-CoV-2, and if possible, further based on the extent of COVID-19 illness. Should this information suggest that it may be reasonable to lower the performance goal for the all subject cohort, negotiation with FDA will be pursued given the FDA guidance document, “Statistical Considerations for Clinical Trials During the COVID-19 Public Health Emergency” dated June 2020.

19.10. **Primary Safety Objective**

Subjects Included the Analysis: Subjects who meet the ITT definition.

Endpoint: The primary safety endpoint is freedom from major adverse events (MAEs) at 30 days post index procedure evaluated per subject. MAEs are defined in **Section 6.1** Primary Endpoints.

Performance Goal: Disease state specific PGs were calculated from the point estimates for major bleeding, pulmonary embolism and peri-procedural mortality from Razavi et al¹ converted to freedom from estimates and application of a 10% non-inferiority margin. For example, the expected freedom from the combined primary safety event for nonthrombotic subjects is $100 - (0.3 + 0.2 + 0.1) = 99.4\%$. Therefore, the PG for the nonthrombotic group is $99 - 10 = 89\%$. The same calculation for the acute-thrombotic group results in an 87% PG, $87\% = 100 - (1.1 + 0.9 + 0.7) - 10$. Lastly, the PG for chronic postthrombotic is $88\% = 100 - (0.9 + 0.6 + 0.3) - 10$. Given the similarity of the disease-state specific PGs, it was determined that a disease state specific goal was not necessary. A PG of 89% was adopted for the study in both the SARS-CoV-2 negative subset and overall.

Hypothesis and Performance Goal:

H₀: Proportion of subjects with freedom from MAE (p_{MAE}) is less than or equal to the (PG) at 30 days, $p_{MAE} \leq 89\%$

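### The primary safety endpoint counts a pulmonary embolism only if CT angiography confirms it, so a PE proven another way in a 30-day completer is scored MAE-free; major bleeds away from the treated vein and access site are also outside the endpoint.

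*Combined protocol and SAP*

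**What the plan says.** The MAE list is the same in the synopsis and in Sections 6.1, 17.4 and 23. Two components matter most here.

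- **PE:** "Clinically significant pulmonary embolism, confirmed by CT angiography". Section 23 does not define clinical significance.
- **Bleeding:** "Device or procedure-related bleed at the target vessel and/or the target lesion or at the access site requiring surgical or endovascular intervention or blood transfusion". The threshold for transfusion is 2 units or more.

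Death is limited to "Device or procedure-related death".

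Section 19.10 sets the goal from a published meta-analysis: "Disease state specific PGs were calculated from the point estimates for major bleeding, pulmonary embolism and peri-procedural mortality". It states no limit on diagnostic method, site or relatedness for these three event types. It subtracts 10 points, obtains 89%, 87% and 88% for the nonthrombotic (NT), acute thrombotic (AT) and chronic postthrombotic (CPT) groups, and adopts 89% for all.

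The numerator in Section 19.10 is the subjects without an MAE within 30 days. The denominator is the subjects with 30 days of follow-up, plus those who left earlier having had an MAE.

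Elsewhere, inclusion criterion 16 (Section 7.4.1) requires "freedom from bleeding and symptomatic pulmonary embolism (confirmed by imaging") after thrombus treatment. Section 12.3 calls for full anticoagulation soon after the procedure and through the 30-day window, and Section 12 allows a documented site alternative. Section 16.1 lists "Gastrointestinal bleed from anticoagulation/antiplatelet medication" among the anticipated risks.

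**The concern.** A PE is a PE whichever test shows it. Nothing in the protocol requires CT angiography when PE is suspected, so the local choice of test can decide whether the same clinical event is a primary endpoint failure. Taken alone, the restriction works in one direction: it moves a real event into the success column.

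The bleeding component has a similar gap. The drugs that the protocol makes the default can cause bleeding anywhere, and the protocol names the gut, yet a bleed there treated with 2 or more units does not count. The observational MAE endpoint from day 30 to 36 months uses the same definition, so the gap persists through follow-up.

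At stake is whether the 30-day safety result covers the events that a reader will take it to cover. The pass limit is a small number of events, so one misclassified subject can matter in a borderline result.

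**Working it through.** **1. Reproduce the plan's figure.** Inputs from Section 19.10: goal 89%, assumed freedom 96.1%, one-sided 2.5%, exact binomial, 90% power. Let X be the number of subjects with an MAE among n = 140.

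- P(X ≤ 8 | failure rate 0.11) = 0.0240
- P(X ≤ 9 | 0.11) = 0.0482
- Pass rule: at most 8 MAEs
- Power: P(X ≤ 8 | 0.039) = 0.902
- Enrollment: 140 / (1 − 0.125) = 160

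The stated 140 and 160 both reproduce. This is a single test; the Hochberg step across the two SARS-CoV-2 cohorts is not modelled.

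**2. Trace how events are scored in Section 19.10.** Assume no other MAE in each row.

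| Event within 30 days | Numerator | Denominator | Scored as |
|---|---|---|---|
| PE confirmed by CT angiography | no | yes | failure |
| Clinically significant PE, other method, completes 30 days | yes | yes | MAE-free |
| Gut bleed treated with 2 or more units, completes 30 days | yes | yes | MAE-free |
| Death judged unrelated | no | no | left out |

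The last row differs from the two above it. That subject is dropped from the primary analysis, and the worst-case analysis in Section 19.7 would impute a failure.

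**3. PE rate behind the goal.** Section 19.10 gives the sums 0.3 + 0.2 + 0.1 (NT), 1.1 + 0.9 + 0.7 (AT) and 0.9 + 0.6 + 0.3 (CPT). Assumption: the figures follow the order in which the events are named, so PE is 0.2%, 0.9% and 0.6%. At least 20% of subjects must come from each group, which gives these extreme mixes:

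- NT/AT/CPT 60/20/20: 0.6×0.2 + 0.2×0.9 + 0.2×0.6 = 0.42%
- 20/20/60: 0.2×0.2 + 0.2×0.9 + 0.6×0.6 = 0.58%
- 20/60/20: 0.2×0.2 + 0.6×0.9 + 0.2×0.6 = 0.70%

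In 160 subjects this is 160 × 0.0042 = 0.7 to 160 × 0.0070 = 1.1 PEs.

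**4. Effect on the test.** Assumptions: true freedom is exactly 89%, and every PE at these rates goes uncounted in a subject with no other MAE. The counted failure rate is 0.11 − h.

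| h (percentage points) | P(X ≤ 8), n = 140 |
|---|---|
| 0 | 2.4% |
| 0.42 | 3.4% |
| 0.58 | 3.8% |
| 0.70 | 4.2% |

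These are upper bounds, because some PEs will be confirmed by CT angiography.

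**5. Features that work the other way.** The MAE list contains four components that are not among the goal's three event types: venous injury, major amputation, stent embolization and new in-stent thrombus. At n = 140 a goal of 89% allows 8 MAEs, against 9 at 88% and 10 at 87%, so the adopted goal is the strictest of the three.

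**The case against.** The strongest reply is that the endpoint as a whole is not lenient. It adds "Presence of new thrombus within the stented segment" and three other components. Section 4.1 puts early thrombosis at 1.5-3%, of the same order as the whole event sum behind the goal (0.6-2.7%), and duplex ultrasound is mandatory at 30 days. The sample size assumes 3.9% MAEs, which is more than the three event types alone. All of this stands. A reader might infer that the trial is biased towards meeting 89%, but the documents do not support that. Each restriction raises observed freedom from MAE, the added components lower it, and the net direction is unknown.

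A reader might also infer that the goal was built from events counted without these limits. Section 19.10 names the event types but does not give the meta-analysis's definitions, so a mismatch can be neither shown nor sized.

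A third tempting reading is that unrelated deaths are scored MAE-free. They are not; they leave the denominator. How the relatedness grades possible and unknown are treated at adjudication may be set out in the CEC Charter, which is not among the documents, so no gap is asserted there.

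On PE, exclusion criterion 2 specifies chest CT, which is closer to the endpoint than criterion 16 is. Subjects with reduced renal function or a manageable contrast allergy may be less likely to have CT angiography, but the documents do not say so, and all subjects receive iodinated contrast at the index venogram. A PE found at autopsy could still count as a related death. Finally, all AEs are reportable (Section 17.1), so these events are recorded.

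None of this changes the scoring in step 2. Counting stent thrombus does not count a missed PE, and recording an AE does not make it an endpoint event.

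**Conclusion.** The point holds as a defect of endpoint definition. A clinically significant PE confirmed by a method other than CT angiography, in a subject who completes 30 days without another MAE, is scored as a success. A bleed treated with 2 or more units away from the target vessel, target lesion and access site is never an MAE. The plan gives no reason for either limit.

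For PE, the most it could do to the test is raise the chance of passing at 140 subjects from 2.4% to 3.4-4.2%. That figure rests on the assumed order of the figures in Section 19.10, on all PEs being uncounted and on true freedom of 89%. No figure is put on the bleeding gap, because the documents give no rate for bleeds at other sites. No stated figure in the plan is wrong, and a claim that the trial is biased overall against its 89% goal goes further than the documents allow.

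**What to change.** **(a)** In the synopsis and in Sections 6.1, 17.4 and 23, word the PE component as: *clinically significant PE confirmed by CT angiography, ventilation-perfusion scan, pulmonary angiography or autopsy*. Leave the rest of the primary composite, the goal and the test unchanged. This alters what is counted, not how a suspected PE is investigated.

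**(b)** In Section 19.10, add one descriptive supportive 30-day rate in all ITT subjects. It counts death from any cause, bleeding at any site that needs intervention or at least 2 units, and any confirmed PE. No test against 89% is needed. Keeping all ITT subjects also brings early unrelated deaths into view.

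**Cost.** Wording in four places, one table, and a few more events for the CEC, all from AEs already collected. Observed freedom from MAE, and with it power, may be slightly lower. As an extreme bound, suppose 96.1% is the rate under the current wording and every PE at the pooled rates is newly counted. Power at n = 140 is then P(X ≤ 8 | 0.039 + h) = 84.7% (h = 0.42 points) to 80.3% (h = 0.70 points), against 90.2%. The real loss should be much smaller, because PEs confirmed by CT angiography already count.

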Stent placement has a high technical success rate and is effective at restoring patency.¹⁷ Technical success of stent placement has been reported to be 84-93% in chronic postthrombotic iliac vein obstruction.¹⁸ Clinical improvement appears to be long lasting.¹⁹ Neglen reported on a group of 982 subjects with chronic nonmalignant obstructive lesions of the femoroiliocaval vein that were stented under IVUS guidance. Primary, assisted primary and secondary patency rates of 57%, 80%, and 86% were achieved at 6 years in thrombotic disease while nonthrombotic rates were 79%, 100%, and 100%, respectively.²⁰ Other smaller studies have reported similar results.^{21,22,23,24,25,26} More recent data reported primary, assisted primary, and secondary patency rates of 93%, 96%, and 100%, respectively,

at 1 year, in the first 30 subjects treated with the Veniti Vici stent²⁷ and 85% primary patency in the first 20 subjects treated with the Zilver Vena stent.²⁸

Adverse Events (AEs) associated with venous stenting have been minimal. The most common complications include early (<30 days) and late thrombosis (1.5-3% and 5%, respectively). Mortality is low, reported at 0-1%.²⁹ Extension of the stent into the IVC is associated with contralateral iliac vein occlusion 1% of the time. However, failure to extend the stent into the IVC when needed may result in an ipsilateral restenosis or occlusion rate of 36%.³⁰ Absolute contraindications listed for ilio caval stenting include uncorrectable coagulopathy and local or systemic infection.³¹

In summary, stenting in chronic ilio caval obstruction is safe and effective. Excellent long-term results with respect to revascularization and symptom relief have been achieved. Recanalization to treat venous claudication with venous stents suggests the highest probability of success.^{32,33}

The Vesper DUO™ Venous Stent System is a new purpose-built stent system that will be studied for use in treating iliac and common femoral vein obstructions due to either nonthrombotic or postthrombotic etiology.

4.2. **Report of Prior Investigations**

This is the first investigation of the DUO Venous Stent System in humans.

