9.4. Questionnaires

9.4.1. **VENous INSufficiency Epidemiological and Economic Study Quality of Life/Symptoms (VEINES-QOL/Sym)**

The VEINES-QOL/Sym scale is a 26-item subject-reported measure that generates 2 separate summary scores for symptoms (VEINES-Sym) and quality of life (VEINES-QOL).

- The VEINES-QOL summary score (25 items) is an estimate of the disease effect on a subject's quality of life
- The VEINES-Sym summary score (10 items) measures the severity of physical symptoms.

This questionnaire must be completed by the subject. Responses are evaluated on a 2-point to 7-point scale that rates intensity, frequency, or agreement.

9.4.2. **EQ-5D-3L**

The EQ-5D-3L instrument includes five dimensions; mobility, self-care, usual activities, pain/discomfort, and anxiety/depression. They each have three levels of categorization. This questionnaire must be completed by the subject.

9.5. **Intravascular Ultrasound Imaging**

IVUS is a very important imaging modality used in conjunction with venography. To some, this is considered the new gold standard in venous imaging. IVUS allows for direct imaging of the vein from an inside-out vantage point with high resolution reproduction of the vessel lumen, vessel wall, and importantly, the extravascular structures in close proximity to the vein. This is particularly useful for detecting iliofemoral compression syndrome, often caused by overriding iliac arteries or mass-effect from other nearby structures (tumors, aneurysms, etc.). Intraluminal filling defects such as acute or chronic thrombus, webs, or spurs are better imaged and identified with IVUS. Additionally, accurate and reproducible direct measurements of vessel diameter (long and short axis) and cross-sectional areas can readily be obtained using IVUS. The typical technique is to insert the IVUS catheter through the lesion and then acquire images as the catheter is pulled back. IVUS runs generally should begin in a normal segment of the vessel cranial to the lesion of interest and terminate in a normal segment caudal to the lesion. It is important to perform a slow and steady pull back of the IVUS catheter.

An IVUS run of the IVC, CIV, EIV, and CFV must be acquired both pre-treatment and post-treatment. Images must be acquired in DICOM format directly from the IVUS equipment for core laboratory analysis.

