IVUS is required at the index procedure, for any reinterventions, and if the 12-month site reported or core laboratory adjudicated DUS shows >50% stenosis or occlusion of the stented segment. In addition, IVUS may be required for the 24 or 36-month DUS shows >50% stenosis or occlusion of the stented segment **and** the subject is symptomatic requiring a reintervention. Operators will be trained on the IVUS protocol provided by the core laboratory. No test cases are required for IVUS. A comprehensive overview for IVUS acquisition requirements can be found in the core laboratory manual.

9.6. **Venographic Imaging**

Venography is an important modality for the assessment and treatment of iliofemoral compression syndrome. A lower extremity vein caudal to the lesion, typically the popliteal vein or mid femoral vein, is accessed and radiopaque iodinated contrast is injected. Images are then captured as the dye flows cranially under digital subtraction angiography (DSA). This allows for the assessment of stenosis of the veins from extrinsic compression/obstruction, and for the detection of acute thrombus and intrinsic vein defects (webbing, spurs, etc.). Angiographic images are typically acquired in the AP view. However, angulated views from the LAO or RAO projections are essential to add additional information about vessel narrowing or “pancaking”, especially when the stenosis is eccentric. This is also useful if the AP view does not demonstrate a narrowing of the vessel. A lack of dye in a venous segment usually represents an occlusion. In the presence of occlusion there are typically numerous collaterals clearly visualized on venography.

A full venographic run of the IVC, CIV, EIV, and CFV must be acquired both pre-treatment and post-treatment. For all venography runs, a radiopaque or marker pigtail catheter should be utilized. This allows for accurate lesion length determination by the core laboratory. Images must be acquired in DICOM format with and without DSA. Full venographic runs, not only still frames, are required for core laboratory assessment.

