15. REQUIRED FOLLOW-UP VISITS AND ASSESSMENTS

All subjects will be required to return for clinic follow-up visits as outlined in **Section 8.1** and in the sections below.

In the event of a public health crisis, a global pandemic, a natural disaster, or any other event which would preclude research sites from conducting research or restrict subjects' ability to attend follow-up visits, guidance will be provided by the Sponsor regarding visit windows.

15.1. 30-day Follow-up Visit (-2 days / +14 days post-Index Procedure)

The following assessments are required to be performed at the 30-day follow-up visit:

- SARS-CoV-2 Testing (if required per Section 9.2)
- DUS
- Venous Ulcer Assessment
- Adverse event assessment
- Review of concomitant medications

15.2. 6-month Follow-up Visit (±30 days post-Index Procedure)

The following assessments are required to be performed at the 6-month follow-up visit:

- SARS-CoV-2 Testing (if required per Section 9.2)
- Venous Ulcer Assessment
- CEAP Classification
- Villalta Score
- VCSS Pain Score
- DUS
- VEINES-QOL/Sym Questionnaire
- EQ-5D-3L Questionnaire
- Adverse event assessment
- Review of concomitant medications

15.3. 12-month Follow-up Visit (±30 days post-Index Procedure)

The following assessments are required to be performed at the 12-month follow-up visit:

- SARS-CoV-2 Testing (if required per Section 9.2)
- Venous Ulcer Assessment
- CEAP Classification

- Villalta Score
- VCSS Pain Score
- DUS
- X-ray of implanted stent(s)
- VEINES-QOL/Sym Questionnaire
- EQ-5D-3L Questionnaire
- Adverse event assessment
- Review of concomitant medications
- Follow-up venogram and IVUS are required if DUS suggests >50% stenosis or occlusion of the stented segment, or if the DUS is non-diagnostic or sub-optimal (i.e., due to obesity). If a follow-up venogram/IVUS is refused by the subject, this must be documented and will not be considered a protocol deviation and the DUS will be used if available.

15.4. **24-month Follow-up Visit (\pm 30 days post-Index Procedure)**

The following assessments are required to be performed at the 24-month follow-up visit:

- SARS-CoV-2 Testing (if required per Section 9.2)
- DUS
- X-ray of implanted stent(s)
- Venous Ulcer Assessment
- CEAP Classification
- Villalta Score
- VCSS Pain Score
- VEINES-QOL/Sym Questionnaire
- EQ-5D-3L Questionnaire
- Adverse event assessment
- Review of concomitant medications

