15.6. Unscheduled Visit

An Unscheduled visit will be documented when a subject presents to the hospital or clinic between study-required follow-up visits and is seen by study personnel for a limb-related event, including reinterventions. The assessments below should be performed prior to any interventional procedures to the target limb. In addition, all imaging studies performed should follow the guidelines set forth by the respective core laboratory. This imaging should be submitted to the respective core laboratories within 3 business days for review and analysis.

- SARS-CoV-2 Testing (if required per Section 9.2)
- Venous Ulcer Assessment (if applicable)
- CEAP Classification
- Villalta Score

- VCSS Pain Score
- VEINES-QOL/SYM Questionnaire
- EQ-5D-3L Questionnaire
- DUS (as clinically indicated)
- Venogram and/or IVUS (as clinically indicated)
- X-ray assessment (as clinically indicated)
- Adverse event assessment
- Review of concomitant medications

Note: Any change in concomitant medications, including any loading dose provided during an unscheduled procedure, should be recorded in the eCRF.

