23. STUDY DEFINITIONS

Term	Definition
Adverse Device Effect (ADE)	An adverse device effect is defined as any untoward adverse event related to the use of an investigational or unintended response to a medical device.
	Note 1: This definition includes adverse events resulting from insufficient or inadequate Instructions for Use, deployment, implantation, installation, or operation, or any malfunction of the investigational medical device
	Note 2: This definition includes any event resulting from use error or from intentional misuse of the investigational medical device.
Adverse Event (AE)	An AE is any untoward medical occurrence, unintended disease or injury, or untoward clinical signs (including abnormal laboratory findings) in subjects whether or not related to the investigational device/procedure.
Allergic Reaction	An allergic reaction characterized by rash, nausea, vomiting, upper respiratory congestion, urticaria, shortness-of-breath, vasovagal reaction, or general collapse (anaphylaxis).
Clinically driven Target Lesion Reintervention (CD-TLR)	Endovascular or surgical procedure for new, recurrent, or worsening symptoms and core lab adjudicated >50% stenosis or occlusion within the stented segment confirmed by diagnostic IVUS
Clinically driven Target Vessel Reintervention (CD-TVR)	Endovascular or surgical procedure performed on the target vessel for new, recurrent, or worsening symptoms
Device Deficiency	Inadequacy of a medical device related to its identity, quality, durability, reliability, safety, or performance, such as malfunction, misuse or not observing the IFU, and inadequate labeling.
Device Malfunction	Failure of a device to meet its performance specifications or otherwise perform as intended.
Device Success	Device Success is defined as:

Term	Definition
	
 • Successful deployment of the DUO Stent(s) at the intended target site, AND • Successful withdrawal of the delivery catheter(s) from the introducer sheath, AND • The DUO Stent remaining at the intended deployment location through completion of the index procedure as determined by the PI
Duplex Ultrasound (DUS)	A form of medical ultrasonography that includes the following elements on the same screen (“duplex”) to facilitate interpretation 1) B-mode, pulsed Doppler display to visualize the structure within a vessel and 2) Color-Doppler display to visualize the blood flow and hemodynamics within a vessel.

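### A stent that occludes before the 12-month window and is reopened without pre-treatment IVUS can be scored primary patent

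*Combined protocol and SAP*

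**What the plan says.** **Endpoint.** Section 6.1 gives two routes to loss of primary patency.

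- *Duplex ultrasound (DUS).* "If site reported or core laboratory adjudicated DUS shows" stenosis above 50% or occlusion, IVUS confirmation is required.
- *CD-TLR.* The procedure must be prompted by symptoms, and the core laboratory must find stenosis above 50% or "occlusion within the stented segment confirmed by diagnostic IVUS". Section 23 defines CD-TLR in the same way. The synopsis and the Section 23 entries for the primary efficacy endpoint and target lesion patency carry the same IVUS condition.

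**Scoring.** Under Section 19.11 a subject is patent with a patent stenosis assessment in the 12-month window (or a later one if none was done in window) and no earlier reintervention meeting the definition. A subject is not patent after such a reintervention, or with a non-patent assessment inside the window. Only subjects classified one way or the other enter the denominator.

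**Imaging at reintervention.** Section 9.5 requires IVUS for every reintervention and describes how it is done: "The typical technique is to insert the IVUS catheter through the lesion and then acquire images as the catheter is pulled back". Section 15.6 says of unscheduled visits: "The assessments below should be performed prior to any interventional procedures to the target limb". Its list, however, gives venogram and/or IVUS only as clinically indicated, and footnote 10 of Section 8.1 has the same qualifier. Section 9.6 requires venography at reinterventions and notes: "A lack of dye in a venous segment usually represents an occlusion".

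**Fallback.** Section 15.3 lets the 12-month DUS stand in for IVUS in one situation: "If a follow-up venogram/IVUS is refused by the subject, this must be documented".

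**The concern.** A complete occlusion is the clearest loss of patency, yet on the reintervention route it counts only if one imaging method confirmed it. IVUS normally runs through the lesion, so in a thrombosed stent it may be obtained only after the clot has been cleared, when it describes the result of treatment rather than the failure. The DUS route does not recover the event, because an occlusion seen before the 12-month window is not a failure in itself.

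The error runs one way: it can only raise observed patency. In a single-arm trial tested against a fixed performance goal, no control arm shares the error, so it acts directly on the type I error.

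The plan also treats the same subject inconsistently. Secondary patency (Section 6.2) presupposes a reintervention for 100% occlusion and puts no IVUS condition on that reintervention. New in-stent thrombus within 30 days is a major adverse event without any IVUS condition. A day-20 stent thrombosis could therefore be a safety failure and an efficacy success.

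**Working it through.** **1. Following one subject through the rules.** The stent occludes with symptoms at month 4. It is reopened on venogram alone, or IVUS is taken after flow is restored and shows 50% stenosis or less.

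- CD-TLR (Sections 6.1 and 23): no IVUS-confirmed stenosis above 50% or occlusion, so not met.
- Non-patent assessment (19.11): the occlusion lies outside the 12-month window, so not met.
- Patent assessment (19.11): DUS in the 12-month window is clean and no qualifying reintervention precedes it, so met.
- Result: primary patent.

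The planned supportive analyses do not correct this. The Kaplan-Meier analysis in 19.11 uses the same reintervention definition. The best-case, worst-case and tipping-point analyses in 19.7 act on missing outcomes, and this subject's outcome is not missing.

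**2. A stent that stays occluded.** There is no patent assessment, so 19.11 cannot score the subject patent. A DUS occlusion inside the window points to failure under 19.11, but Section 6.1 asks for IVUS confirmation and Section 15.3 waives it only for refusal. If IVUS is infeasible, the subject may be left unclassified and drop from the denominator.

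**3. Reproducing the plan's power.** Inputs from 19.11: N = 128; performance goals 0.83, 0.70 and 0.66 (nonthrombotic, acute thrombotic, chronic postthrombotic); planned patency 0.96, 0.87 and 0.79; one-sided 2.5%; success when Z > 1.96 with variance under the null. Equal thirds is taken as 43/43/42.

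- Pooled goal = (43×0.83 + 43×0.70 + 42×0.66)/128 = 93.51/128 = 0.7305
- SE = √(43×0.83×0.17 + 43×0.70×0.30 + 42×0.66×0.34)/128 = √24.52/128 = 0.0387
- Boundary = 0.7305 + 1.96×0.0387 = 0.8064, or 103.2 of 128, so success needs at least 104 patent (at most 24 failures)

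The exact distribution of the patent count is the sum of three binomials. At the planned rates, P(count ≥ 104) = 98.5%, against the plan's 98%.

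**4. Effect on type I error.** With each state at its goal, expected failures are 128 − 93.51 = 34.5. If k true failures are scored patent, the trial passes whenever the true patent count is at least 104 − k:

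| k scored patent | P(pass) at the goal |
|---|---|
| 0 | 1.9% |
| 1 | 3.2% |
| 2 | 5.0% |
| 3 | 7.7% |
| 4 | 11.2% |

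Four subjects are 4/34.5, about 12% of the failures expected at the goal. The table concerns a single test in all subjects and leaves out the Hochberg step with the SARS-CoV-2 negative subset. Over the ten mixes in the plan's power table, the k = 0 value runs from 1.9% to 2.8%, so equal thirds is the mix with the most slack.

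**The case against.** **The plan has safeguards.** Section 9.5 requires IVUS at any reintervention, and both Section 15.6 and footnote 9 of Section 8.1 place unscheduled assessments before intervention. If these are followed, or if IVUS after reopening still shows more than 50% stenosis, the event counts. This stands, and it limits the problem to cases without pre-treatment IVUS. But the as-indicated wording in Section 8.1 and the and/or in Section 15.6 make a venogram-only reintervention compatible with the protocol, and nothing says how to score it.

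**IVUS in an occluded vein is not impossible.** A reader might infer that IVUS can never be obtained in an occluded stent. The documents do not say so. Section 9.5 describes a typical technique. The index procedure requires pre-treatment IVUS in a population that includes total occlusions (Sections 9.3.1 and 13.1).

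**An occlusion that cannot be crossed is not scored patent.** A reader might also infer that it is. As step 2 shows, 19.11 does not allow this while the stent stays closed. If the subject is unclassified, the worst-case and tipping-point analyses apply.

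**Reopened occlusions are visible elsewhere.** Clinically driven target vessel reintervention has no IVUS condition, and major adverse events are reported to 36 months. That helps a reader of the results but does not change the primary test.

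**The size is not anchored.** Section 4.1 reports: "The most common complications include early (<30 days) and late thrombosis (1.5-3% and 5%, respectively"). The late figure has no 12-month limit, and nothing says how many such stents would be reopened without IVUS. Larger error rates, from assuming that 20% or 30% of all failures escape, have no basis in the documents and would include partial stenoses that IVUS can confirm.

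**Conclusion.** The concern holds for one defined case: a symptomatic occlusion before the 12-month window, reopened without pre-treatment IVUS (or with IVUS only afterwards, showing 50% stenosis or less), and patent at 12 months. The written rules score that subject primary patent. A lesser gap concerns the stent that stays occluded when IVUS is infeasible: it has no clear classification and may leave the denominator.

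The number of subjects is unknown. Under the stated assumptions (128 evaluable, equal thirds, each state at its goal, one test in all subjects), a single misclassified occlusion takes the one-sided error from 1.9% to 3.2%, past the planned 2.5%, and four take it to 11.2%. These figures show how sensitive the test is; they do not predict what will happen. The correction should be made because a few subjects are enough and the images needed are already collected.

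**What to change.** 1. **Definitions.** In the synopsis, Section 6.1, and the Section 23 entries for CD-TLR, the primary efficacy endpoint and target lesion patency, state that a complete occlusion may be confirmed by diagnostic IVUS or, when pre-treatment IVUS was not obtained or not feasible, by a pre-treatment venogram or DUS read by the core laboratory. Add that IVUS taken after reopening cannot overturn that finding. Keep the IVUS requirement for partial stenosis.
2. **Section 19.11.** No edit is needed. The primary and Kaplan-Meier rules point to the definition and follow it.
3. **Section 15.3.** Extend the DUS fallback from refusal to cases where IVUS is infeasible and DUS shows occlusion.
4. **Sections 9.5 and 15.6.** Reconcile what they say about IVUS at reintervention, together with footnotes 9 and 10 of Section 8.1.

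**Cost.** Endpoint wording only. Venography is already required at reinterventions (Section 9.6), and target-limb images already go to the core laboratory (Section 8.1, footnote 11). Observed patency may be slightly lower. If the planned rates do not already count such events, four extra failures would take exact power at equal thirds from 98.5% to 88.1%; if they do, power is unchanged.
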